18.4.1. LABORATORY REFERENCE RANGES AND MARKEDLY ABNORMAL CRITERIA

Quantitative laboratory measurements will be compared with the relevant laboratory reference ranges in SI units and categorized as:

Low: Below the lower limit of the laboratory reference range.

Normal: Within the laboratory reference range (upper and lower limit included).

High: Above the upper limit of the laboratory reference range.

In addition to the high and low quantitative laboratory assignments, Hy's law criteria ($\geq 3 \times \text{ULN}$ for either ALT or AST, with accompanying total bilirubin $> 2 \times \text{ULN}$ in the absence of other known causes) will be used to identify potential Hy's law cases.

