11.1.6.3.3. Monitoring and Management of Hemoglobin Change

If at any time after randomization a patient experiences a decrease >2.0 g/dL (20 g/L) from baseline (Week 0 [Visit T1]), the patient will undergo repeat confirmatory hematology testing as soon as is reasonably possible, preferably within 3 to 7 days of the laboratory result becoming available.

Repeat hematology assessment will include: 1) measurement of Hgb, hematocrit (Hct), mean corpuscular hemoglobin, mean corpuscular hemoglobin concentration, mean corpuscular volume, platelet count, reticulocyte count (percent and absolute), red blood cell count (RBC), and white blood cell count (WBC) with differential (absolute values only); 2) history of concomitant medication use; and 3) query for related symptoms. Additionally, further testing may be warranted to rule out additional pathology depending on clinical presentation, and should be discussed with Esperion Therapeutics personnel or the authorized Medical Monitor.

- If repeat Hgb assessment confirms a decrease >2.0 g/dL (20 g/L) from baseline, the patient should be monitored carefully during the study and return at 2-week intervals after study completion for additional Hgb measurement until the level returns to baseline or reaches a stable level.
- If repeat Hgb assessment confirms Hgb <8 g/dL (80 g/L), the patient should be withdrawn from IMP treatment. The patient will return at 1-week intervals after withdrawing from IMP treatment for additional Hgb measurement until the level returns to baseline or reaches a satisfactory conclusion.
- If the patient is withdrawn from IMP treatment, the patient should be asked to continue being followed for safety using the protocol-specified visit schedule (see [Appendix 1](#)).

At any time, the investigator may choose to consult with a specialist to further evaluate the cause of the alteration in Hgb.

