12.8. Safety Endpoints

The summarization of AEs will include TEAEs. TEAEs and SAEs will be summarized by SOC, severity, and relationship to study drug for each treatment group. These AE summaries will include cumulative incidence (percent of patients experiencing the AE) and patient-year adjusted incidence rates. If appropriate, absolute and relative risk differences will be calculated using both cumulative incidence and incidence rates. Deaths, withdrawal from study treatment due to AEs, and withdrawal from the study due to AEs will each be summarized by treatment group.

Clinical safety laboratories, including hematology, blood chemistry, coagulation, HbA_{1C}, glucose, and urinalysis; PE findings; vital signs; ECG readings; and weight will be summarized by the value and by change from baseline in the value (where appropriate) at each postbaseline time point.

Hepatic Safety

Liver-associated enzymes and TB will be summarized by the value and change from baseline in the value, by treatment group and visit. In addition, the number and percent of patients with abnormal values for ALT, AST, and TB will be summarized. These summaries of patients with abnormal values will be performed overall; by normal baseline; and by abnormal baseline for each of ALT, AST, and TB. Hy's law criteria ($\geq 3 \times$ ULN for either ALT or AST, with accompanying TB $> 2 \times$ ULN or patient's baseline) will also be applied to the data; any potential Hy's law cases will be listed separately. In the case of patients with Gilbert's disease, TB will be fractionated and the determination of $2 \times$ ULN based upon direct (conjugated) bilirubin. For patients with Gilbert's Disease $2 \times$ the conjugated bilirubin will be used as the criterion.

Musculoskeletal Safety

AEs of muscle-related symptoms will be summarized by treatment group. CK levels will be summarized by the value and change from baseline in the value, by treatment group and visit. In addition, the number and percent of patients with abnormal CK values will be summarized. These summaries of patients with abnormal CK will be performed overall; by normal baseline CK; and by abnormal baseline CK.

Diabetes and Hyperglycemia

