18.4. SAFETY LABORATORY EVALUATIONS

Results from the central laboratory will be included in the reporting of this study for Hematology, Blood Chemistry, Lipids, Coagulation, HbA1C, hsCRP and Urinalysis. A list of laboratory assessments to be included in the outputs is included in Protocol, Section 11.1.6.1.

Presentations will use SI Units and conventional units.

Quantitative laboratory measurements reported as “< X”, i.e. below the lower limit of quantification (BLQ), or “> X”, i.e. above the upper limit of quantification (ULQ), will be converted to X for the purpose of quantitative summaries, but will be presented as recorded, i.e. as “< X” or “> X” in the listings.

The formula to calculate eGFR is: $eGFR = 186 \times (\text{Creatinine} / 88.4)^{-1.154} \times (\text{Age})^{-0.203} \times (0.742 \text{ if female}) \times (1.210 \text{ if black})$, where creatinine is in mmol/L.

Summaries for all lab results, including unscheduled visit values, will be included for below analyses:
 Observed and change/percent change from baseline by visit (for quantitative measurements).

Shift from baseline by visit according to normal ranges.

Shift from baseline according to normal ranges for HbA1c and glucose by history of diabetes and visit.
 eGFR and values of CK will be summarized by treatment group and by baseline eGFR categories (low, normal, high).

Potential Hy’s law cases (>3 × ULN for either ALT or AST AND Total Bilirubin >2 × ULN in the setting of no known other cause) will be tabulated and listed.

Laboratory abnormalities in parameters of interest

- ALT or AST (> 3x ULN , >5xULN)
- TB (>2x ULN)
- CK (> 5x ULN) and (>10x ULN)
- Fasting Blood Glucose (≤50 mg/dL, ≥126 mg/dL) by history of diabetes
- HbA1c (≥6.5%) by history of diabetes
- Creatinine (change from baseline for >1 mg/dL)
- eGFR (< 15 mL/min/1.73m², 15 –< 30 mL/min/1.73m²)
- Hgb (decrease from baseline for ≥2 g/dL)
- Hgb (<8 g/dL)

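### The SAP's Hy's law definition differs between 18.4 and 18.4.1, and departs from Protocol 12.8 by adding a cause filter and omitting the Gilbert's rule

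*SAP*

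**What the plan says.** Three passages define the criterion for analysis.

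- **SAP 18.4** gives the rule for the table and listing: ">3 × ULN for either ALT or AST AND Total Bilirubin >2 × ULN in the setting of no known other cause".
- **SAP 18.4.1** sets the aminotransferase limit at 3 × ULN or more "for either ALT or AST, with accompanying total bilirubin" above 2 × ULN, again only "in the absence of other known causes) will be used to identify potential Hy's law cases".
- **Protocol 12.8** (and the synopsis) uses 3 × ULN or more for ALT or AST, with total bilirubin (TB) above 2 × ULN or judged against the patient's own baseline. It sets no condition on cause and states that "any potential Hy's law cases will be listed separately". For Gilbert's disease, "TB will be fractionated and the determination of" the 2 × ULN limit rests on direct bilirubin. Section 12.8 then adds a second Gilbert's sentence that refers to twice the conjugated bilirubin and names no ULN.

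Three other provisions bear on this. Protocol 7.2, exclusion 8, lets patients with Gilbert's disease enroll. Protocol 12.1 gives the SAP precedence over the protocol for data analysis. Protocol Table 5 has direct bilirubin in the routine chemistry panel.

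**The concern.** Precedence of the SAP over the protocol cannot settle a disagreement between two SAP sections, so the aminotransferase limit is open.

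The cause condition acts before anything is counted, because in 18.4 only cases "in the setting of no known other cause) will be tabulated and listed" reach the output. The SAP does not say who judges cause, from which data, or whether treatment is masked. The clinical events committee covers deaths and cardiovascular events only (Protocol 11.6, SAP 18.3). SAP 4.2 places the final analysis after unblinding, so nothing in the plan prevents cause from being judged with treatment known.

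On Gilbert's disease the SAP is silent, so a programmer cannot tell whether the protocol's direct-bilirubin rule still applies.

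The liver was a target organ in rats and monkeys (Protocol 4.2.2). Protocol 11.4 reports seven earlier patients on bempedoic acid with confirmed ALT or AST above 3 × ULN. A joint aminotransferase-plus-bilirubin signal is the one a reader of the safety results will look for.

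**Working it through.** The documents state no count for this criterion, so there is no figure to reproduce. The check applies each rule to boundary profiles. All values are multiples of ULN.

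**Rules**

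- SAP 18.4: ALT or AST > 3, TB > 2, no other known cause.
- SAP 18.4.1: ALT or AST ≥ 3, TB > 2, no other known cause.
- Protocol 12.8: ALT or AST ≥ 3, and TB > 2, or direct bilirubin > 2 in a Gilbert's patient. The baseline alternative is left out because its wording does not say whether it means above baseline or above twice baseline. Either reading could only add cases.

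| Profile | SAP 18.4 | SAP 18.4.1 | Protocol 12.8 |
|---|---|---|---|
| (a) ALT 3.0, TB 2.5, no other cause | no | yes | yes |
| (b) ALT 3.5, TB 2.5, no other cause | yes | yes | yes |
| (c) ALT 3.5, TB 2.5, other cause recorded | no | no | yes |
| (d) Gilbert's, ALT 3.5, TB 2.5, direct 1.0, Gilbert's not taken as the cause | yes | yes | no |
| (e) Gilbert's, ALT 3.5, TB 3.5, direct 2.2, Gilbert's taken as the cause | no | no | yes |

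The two SAP sections part only in (a). Profile (c) shows the effect of the filter. Profiles (d) and (e) show the Gilbert's gap over-counting and under-counting relative to the protocol.

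**How often profile (a) could arise.** The documents give no ALT distribution, so this is an assumption: peak ALT lognormal with median 0.6 × ULN and log-SD 0.4 or 0.6, whole-number results, ULN 33, 40 or 55 U/L. With X the peak ALT:

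tie share = [P(X ≥ 3·ULN − 0.5) − P(X ≥ 3·ULN + 0.5)] / P(X ≥ 3·ULN − 0.5)

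| ULN (U/L) | log-SD 0.4 | log-SD 0.6 |
|---|---|---|
| 33 | 10.2% | 4.9% |
| 40 | 8.5% | 4.1% |
| 55 | 6.2% | 3.0% |

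For ULN 40 and log-SD 0.6 the two probabilities are 0.00373 and 0.00358. Per 500 patients that is 500 × 0.00373 ≈ 1.9 at or above the limit and 500 × 0.00015 ≈ 0.08 exactly on it, before requiring TB above 2 × ULN. The tie is therefore real but rare.

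The filter and the Gilbert's gap cannot be sized. The documents give neither the prevalence of Gilbert's disease in this population nor the frequency of alternative causes.

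**The case against.** The strongest reply has three parts.

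**Patients removed by the filter do not vanish.** SAP 18.4 counts ALT or AST above 3 × and 5 × ULN, and TB above 2 × ULN, with no cause condition. Shift tables include unscheduled values, SAP 6.3 lists retests, and Protocol 11.1.6.3.1 requires a work-up of new elevations above 3 × ULN. This stands, and it rules out the reading that such cases disappear from the report. It does not supply the joint count: separate ALT/AST and TB categories do not show that both occurred in the same patient. The ALT/AST category is also strictly above 3 × ULN, so profile (a) is missing there too. The SAP addendum lists a post-hoc liver function table, but only its title is given.

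**Most of the differences are not contradictions within the SAP.** This is correct. The filter is in both sections, the Gilbert's rule is in neither, and Protocol 12.1 lets the SAP depart from the protocol. Only the aminotransferase limit conflicts inside the SAP. What remains is that the filter is undefined, and that silence on Gilbert's disease does not say whether the protocol rule was replaced.

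**The Gilbert's effect need not lose cases.** Also correct: profile (d) is counted by the SAP and not by the protocol, and profile (e) needs someone to record Gilbert's disease as the cause.

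A reader might extend the point to hemoglobin. SAP 18.4 tabulates "Hgb (decrease from baseline for ≥2 g/dL", while Protocol 11.1.6.3.3 acts when a patient "experiences a decrease >2.0 g/dL (20 g/L) from baseline". The documents do not support calling this an analysis error. The protocol figure triggers repeat testing, Protocol 12.8 sets no category for hemoglobin fall, the SAP states its limit once, and that limit includes every fall above 2.0 g/dL.

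**Conclusion.** The Hy's law definition needs correcting. The SAP disagrees with itself on the ALT/AST limit. It also departs from Protocol 12.8 by adding an undefined cause filter ahead of tabulation and by omitting the Gilbert's rule and the baseline alternative.

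The internal conflict changes a count only at exactly 3 × ULN, about 3% to 10% of patients at or above that limit under the assumed distributions. The filter and the Gilbert's gap matter more, because either can move a count that is likely to be very small, and the Gilbert's gap can move it up or down. Their size is unknown.

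Two stronger readings should not be drawn: that the SAP's safety-laboratory criteria conflict with each other generally, and that the hemoglobin table is wrong.

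**What to change.** 1. Put one laboratory-only screen in both SAP 18.4 and 18.4.1, aligned with Protocol 12.8: ALT or AST at or above 3 × ULN with TB above 2 × ULN, using direct bilirubin for Gilbert's patients.
2. Reconcile two unclear items in Protocol 12.8 and state the outcome in the SAP: what the baseline alternative for bilirubin means, and how the second Gilbert's sentence, which has no ULN, relates to the first.
3. Tabulate and list every patient who meets the screen. Record the cause assessment beside each one, naming who makes it and from what data, blinded to treatment.
4. At most, footnote the hemoglobin table to say that its category differs from the repeat-test trigger in Protocol 11.1.6.3.3.

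The cost is SAP wording and a rerun of a few safety outputs. No new data are needed. The addendum of 17 December 2018 says that the planned analyses were completed and that further outputs followed unblinding. Corrected outputs should therefore be labelled as such, and cause should be assessed by someone who has not seen the allocation.

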18.5. ECG EVALUATIONS

The Investigator's judgment of overall assessment of ECG (Normal, Abnormal, Not Clinically Significant (ANCS), and Abnormal, Clinically Significant (ACS)) will be recorded at baseline and end of study. A summary of shift from baseline to end of study in overall assessment will be provided.

18.6. VITAL SIGNS

The following Vital Signs measurements will be reported for this study:

- Sitting Systolic Blood Pressure (mmHg)
- Sitting Diastolic Blood Pressure (mmHg)
- Sitting Heart Rate (bpm)
- Weight (kg)
- Height (cm) (at Screening only)
- BMI (kg/m²) (calculated automatically by the EDC system)

The following summaries will be provided for vital signs data:

- Observed and change from baseline by visit

18.7. PHYSICAL EXAMINATION

Abnormalities in physical examinations will be presented in a listing.

18.8. PHARMACOKINETICS

A PK blood sample will be collected prior to dosing at Weeks 24 and 52. Descriptive statistics for concentrations of bempedoic acid and its metabolite ESP15228 will be presented for each visit for the PK Analysis Set as defined in section 5.4. All concentration data will also be presented in a listing.

All concentrations below the limit of quantification or missing data will be labelled as such in the concentration data listings. Concentrations below the lower limit of quantification will be treated as zero in summary statistics.

PK observations with missing concentration, missing dose, missing elapsed time will be flagged as such in the concentration data listings and excluded from PK statistical summary.

19. DATA NOT SUMMARIZED OR PRESENTED

The other variables and/or domains not summarized or presented are:

- Comments
- Variables used by the data entry system to direct user to proper page (e.g., patient visit status, patient health status)
- Inclusion/Exclusion Criteria that are not violated
- Normal Physical Examination Results

These domains and/or variables will not be summarized or presented, but will be available in the clinical study database, SDTM and/or ADaM datasets.

[REDACTED]

[REDACTED]

[REDACTED]

[REDACTED]

Version Number:
Version Date:

0.5
14June2018

APPENDIX 1. PROGRAMMING CONVENTIONS FOR OUTPUT

QUINTILES OUTPUT CONVENTIONS

OUTPUT FILE NAMING CONVENTIONS

File names should only consist of uppercase letters, lowercase letters, digits (0 to 9) and underscores. A period should only be used to indicate a separator between the file name and the extension. No spaces, other special characters or punctuation marks are permitted.

As far as possible, output files should be in RTF format, although .DOC files are also permitted.

The program, program log and output file name should reflect the type and number of the statistical output. If this is not possible, then the output name should be at least as descriptive as possible. A prefix can be used to distinguish between a Table, Listing and Figure document ('T' for table, 'L' for listing and 'F' for figure). If there is only 1 digit in the number of the table, listing or figure in the place where 2 digits are possible, a leading zero should be added in the file name to make sorting consistent with the sequence (eg T14_3_01_1.RTF)

PAPER SIZE, ORIENTATION AND MARGINS

The size of paper will be Letter for the United States, otherwise A4.

The page orientation should preferably be landscape, but portrait is also permitted.

Margins should provide at least 1 inch (2.54 centimeters) of white space all around the page, regardless of the paper size.

The number of columns per page (linesize) should be 145 for A4 and 134 for Letter.

The number of rows per page (pagesize) should be 49 for A4 and 51 for Letter.

Statistical Analysis Plan

FONTS

The font type ‘Courier New’ should be used as a default for tables and listings, with a font size of 8. The font color should be black. No **bolding**, underlining *italics* or subscripting should be permitted. Try to avoid using super-scripts, unless absolutely necessary. Single spacing should be used for all text. Figures should have a default font of “Times Roman”, “Helvetica”, or “Courier New” .

This can be achieved by using the following options in SAS:

```
goptions
gunit = pct
cback = white
colors = (black)
hby = 2.4
ftext = "TimesRoman"
htext = 2.5
device = cgmof97l
gaccess = gsasfile;
filename gsasfile "....cgm";
```

HEADER INFORMATION

Headers should be defined as follows:

- The header should be placed at the top of the page (same place on each page) regardless of the size or orientation of the table or listing
- The customer name and protocol number should appear in row 1, left-aligned
- The output identification number should appear in row 2, centered
- The output title should start in row 3, centered
- The output population should appear in row 4, centered. The population should be spelled out in full, e.g. Intention-to-Treat in preference to ITT.
- Row 5 should be a continuous row of underscores (‘_’) (the number of underscores should equal the linesize)
- Row 6 should be a blank line
- Mixed case should be used for titles
- The output titles should be designed so that they are arranged consistently through all outputs. For example, content (eg Vital Signs) followed by metric (eg Change from Baseline) e.g. Vital Signs – Change from Baseline.
- Titles should not contain quotation marks or footnote references
- The column headings should be underlined with a row of underscores (‘_’)
- Column headings spanning more than one column should be underlined and have underscores on either side of the title and should be centered
- Column headings containing numbers should be centered
- Column headings should be in sentence case
- In general, the population count should appear in the column header in the form “(N=XXX)”

Statistical Analysis Plan

- “Statistic” should be the column header over n, Mean, SE, n (%) etc.
- As a rule, all columns should have column headings.

TABLE AND LISTING OUTPUT CONVENTIONS

General:

- The first row in the body of the table or listing should be blank
- The left hand column should start in column 1. No indenting or centering of the output should occur.
- Rounding should be done with the SAS function ROUND.
- Numbers in tables should be rounded, not truncated.
- Alphanumeric output should be left aligned.
- Numbers should be decimal point aligned.
- Whole numbers should be right aligned.
- Text values should be left aligned.
- The first letter of a text entry should be capitalized
- Listings of adverse events, concomitant medications, medical histories etc. should be sorted in chronological order, with earliest adverse event, medication or history coming first.
- The study drug should appear first in tables with treatments as columns
- In general, only present totals (across treatment groups) at baseline/randomization, and do not present them post randomization, unless the customer specifically requests it.
- If possible, include 100% frequencies in the table shell, so that it is clear what the denominator is for percentage calculations.
- All listing outputs should be sorted (preferably by Treatment, Site Number and Subject Number).
- Do not use superscripts and subscripts
- Exponentiation will be expressed using a double asterisk, i.e., mm³ will be written as mm**3.
- All variables that are output in the CRF (which have data present) should appear in the listings, along with all derived data appearing in the corresponding tables
- The width of the entire output should match the linesize

Univariate Statistics:

- Statistics should be presented in the same order across tables (i.e., n, Mean, SD, Q1, Median, Q3, Minimum, Maximum)
- Table statistics should line up under the N part of the (N=XXX) in the table header. All decimal points should line up. If the minimum and maximum are output on one line as Minimum, Maximum then the comma should line up with the decimal point.
- If the original data has N decimal places, then the summary statistics should have the following decimal places:
 - Minimum and maximum: N
 - Mean, median and CV%: N + 1
 - SD: N + 2

Statistical Analysis Plan

Frequencies and percentages (n and %):

- Percent values should be reported inside parentheses, with one space between the count and the left parenthesis of the percentage. Parentheses should be justified to accept a maximum of 100.0 as a value and padded with blank space if the percent is less than 100.0. An example is given below:

77 (100.0%)
 50 (64.9%)
 0 (0.0%)

- Percentages will be reported to one decimal place, except percents <100.0% but >99.9% will be presented as '>99.9%' (e.g., 99.99% is presented as >99.9%); and percents < 0.1% will be presented as '<0.1%' (e.g., 0.08% is presented as <0.1%). Rounding will be applied after the <0.1% and >99.9% rule.

Eg (<0.1%)
 (6.8%)
 (>99.9%)

Percentages may be reported to 0 decimal places as appropriate (for example, where the denominator is relatively small).

- Where counts are zero, percentages of 0.0% should appear in the output.

Confidence Intervals:

- As a rule confidence intervals are output to one place more than the raw data, and standard deviations and standard errors to two places more than the raw data
- Confidence intervals should be justified so that parentheses displayed on consecutive lines of a table "line up".
- Boundary values of confidence intervals should be separated by a comma.
- Boundary values should be padded as necessary to accept negative values and to allow alignment of the decimal place.
- An example is given below:

(-0.12, -0.10)
 (9.54, 12.91)

P-values:

- P-values should be reported to three decimal places, except values <1.000 but >0.999 will be presented as '>0.999' (e.g., 0.9998 is presented as >0.999); and values <0.001 will be presented as '<0.001' (e.g., 0.0009 is presented as <0.001). Rounding will be applied after the <0.001 and >0.999 rule

Ratios:

- Ratios should be reported to one more decimal place than the original data.

Spacing:

- There must be a minimum of 1 blank space between columns (preferably 2)

Statistical Analysis Plan

Denominators:

- If a different count other than the population count is used for a denominator (within the table) to calculate percentages, there should be a row in the table that identifies that number “n”.
- Alternatively, a footnote should be included in each table with percentages to indicate the denominator for percentages.

Missing values

- A “0” should be used to indicate a zero frequency.
- A blank will be used to indicate missing data in an end-of-text table or subject listing.

FIGURE OUTPUT CONVENTIONS

- Figures should be provided in RTF files using the SAS Output Delivery System (ODS), as Computer Graphics Metafile (CGM) formatted graphical output generated by SAS.
- The CGM file itself should contain the title or footer.
- The image should be clear and of high quality when viewed in the Word document, and when printed.
- In general, boxes around the figures should be used.

FOOTNOTE INFORMATION

Footers should be defined as follows:

- A continuous line of underscores (‘_’) will follow the body of the table or listing prior to any footnotes at the bottom of the page
- Table footnotes should be defined using compute statements in the proc report, and should appear directly after the body of the table
- The program path and name and version number (if applicable) should appear as footnote 1 at the bottom of the page
- The date/time stamp should appear as footnote 2 at the bottom of the page
- Footnotes should be left-aligned.
- Footnotes should be in sentence case.
- Only “typewriter” symbols are permitted – eg “*”, “\$”, “#”, “@”, “&” and “+”.
- The choice of footnote symbols should be consistent. E.g. if you have the footnote “# indicates last observation carried forward” for one table, the same symbol and footnote should indicate LOCF for all tables.
- If text wraps across more than one line (for a note), the first letter for all lines of text after the first one will be indented to align beneath the first letter of the text in the first line.
- The page identification in the format Page X of Y (where Y is the total number of pages for the output) should appear in the first footnote, right aligned

Ordering of footnotes should be as follows:

- 1.) Source data listing reference, if necessary

Statistical Analysis Plan

- 2.) Abbreviations and definitions
- 3.) Formulae
- 4.) P-value significance footnote
- 5.) Symbols
- 6.) Specific notes
 - Common notes from table to table should appear in the same order.
 - The symbols should appear in the same order as what they are defined in the table or listing, from left to right.

PROGRAMMING INSTRUCTIONS

Programming instructions must appear in blue font at the end of each table or listing shell. Programming instructions, where necessary, should follow the table or listing shells in blue font, beginning with the words “Programming Note” followed by a colon. These include notes on the output, reminders of how to handle missing values, repeat shells for similar tables etc.

DATES & TIMES

Depending on data available, dates and times will take the form yyyy-mm-ddThh:mm:ss.

PRESENTATION OF TREATMENT GROUPS

For outputs, treatment groups will be represented as follows and in that order:

Treatment Group	For Tables and Graphs	For Listings
Placebo	Placebo	Placebo
Bempedoic Acid 180 mg	Bempedoic Acid 180 mg	Bempedoic Acid 180 mg
Not Randomized	Not Randomized	Not Randomized

PRESENTATION OF VISITS

For outputs, visits will be represented as follows and in that order:

Long Name (default)	Short Name
Week -5 (Visit S1)	W-5 (VS1)
Week -4 (Visit S2)	W-4 (VS2)

